## **5.5 Criteria for Temporarily Delaying the Enrollment/Randomization/Administration of Study Intervention Administration**

Not applicable.

## **6 Study Intervention(s) and Concomitant Therapies**

Study intervention is any investigational intervention(s), marketed product(s), placebo, or medical device(s) intended to be administered to a study participant per the study protocol.

### **6.1 Study Intervention(s) Administration**

Arm Name:	1-Day M5717 plus Pyronaridine Safety/PK Assessment Run-in Cohort (Part A)	1-Day M5717 plus Pyronaridine Safety/PK Assessment Run-in Cohort (Part A)	1-Day M5717 plus Pyronaridine (Part B: Cohort B0 and B1)	1-Day M5717 plus Pyronaridine (Part B: Cohort B0 and B1)	2-Day M5717 plus Pyronaridine (Part B: Cohort B2)	2-Day M5717 plus Pyronaridine (Part B: Cohort B2)	3-Day Pyronaridine- artesunate (Pyramax) (Part B: Cohort B3)
Arm Type:	Experimental	Experimental	Experimental	Experimental	Experimental	Experimental	Active Comparator
Arm Description:	M5717 plus pyronaridine once daily in a single day treatment regimen	M5717 plus pyronaridine once daily in a single day treatment regimen	M5717 plus pyronaridine once daily in a single day treatment regimen	M5717 plus pyronaridine once daily in a single day treatment regimen	M5717 plus pyronaridine once daily in a 2-day treatment regimen	M5717 plus pyronaridine once daily in a 2-day treatment regimen	Pyronaridine- artesunate (Pyramax) once daily in a 3-day treatment regimen
Intervention Name:	M5717	Pyronaridine	M5717	Pyronaridine	M5717	Pyronaridine	Pyronaridine- artesunate (Pyramax)
Type:	Drug	Drug	Drug	Drug	Drug	Drug	Drug
Dose Formulation:	Granule to be dispersed in water	Tablet	Granule to be dispersed in water	Tablet	Granule to be dispersed in water	Tablet	Tablet
Unit Dose Strength(s):	100 mg capsules, 30 mg capsules	180 mg tablets	100 mg capsules, 30 mg capsules	180 mg tablets	100 mg capsules, 30 mg capsules	180 mg tablets	180/60 mg fixed-dose combination
Dose Amount:	330 mg	360 mg	Adults and adolescents ≥ 45 kg: 660 mg, Adolescents < 45 kg: 500 mg	≥ 24 to < 45 kg: 360 mg, ≥ 45 to < 65 kg: 540 mg, ≥ 65 kg: 720 mg	Adults and adolescents ≥ 45 kg: 660 mg, Adolescents < 45 kg: 500 mg	≥ 24 to < 45 kg: 360 mg, ≥ 45 to < 65 kg: 540 mg, ≥ 65 kg: 720 mg	≥ 24 to < 45 kg: 360/120 mg, ≥ 45 to < 65 kg: 540/180 mg, ≥ 65 kg: 720/240 mg
Frequency:	1-day treatment regimen	1-day treatment regimen	1-day treatment regimen	1-day treatment regimen	2-day treatment regimen	2-day treatment regimen	3-day treatment regimen
Route of Administration:	Oral, fasting conditions	Oral, fasting conditions	Oral, fasting condition	Oral, fasting conditions	Oral, fasting condition	Oral, fasting conditions	Oral, fasting conditions
IMP/NIMP:	IMP	IMP	IMP	IMP	IMP	IMP	IMP
Sourcing	M5717 will be provided by the Sponsor	CCI [REDACTED] [REDACTED]	[REDACTED] [REDACTED]	[REDACTED] [REDACTED]	[REDACTED] [REDACTED]	[REDACTED] [REDACTED]	[REDACTED] [REDACTED]

Packaging and Labeling	Study intervention M5717 will be provided in study-specific, uniquely labelled Alu/Alu blisters, respectively. Each blister will be labeled per country requirement.	Study intervention pyronaridine will be provided in study-specific, uniquely labelled Alu/Alu blisters, respectively. Each blister will be labeled per country requirement.	Study intervention M5717 will be provided in study-specific, uniquely labelled Alu/Alu blisters, respectively. Each blister will be labeled per country requirement.	Study intervention pyronaridine will be provided in study-specific, uniquely labelled Alu/Alu blisters, respectively. Each blister will be labeled per country requirement.	Study intervention M5717 will be provided in study-specific, uniquely labelled Alu/Alu blisters, respectively. Each blister will be labeled per country requirement.	Study intervention pyronaridine will be provided in study-specific, uniquely labelled Alu/Alu blisters, respectively. Each blister will be labeled per country requirement.	Pyramax will be provided in study-specific, uniquely labeled Alu/Alu blisters. Each blister will be labeled per country requirement.
Current/Former Name(s) or Alias(es)	M5717: MSC2576186A		M5717: MSC2576186A		M5717: MSC2576186A		

## 6.2 Study Intervention(s) Preparation, Handling, Storage, and Accountability

The Investigator, institution, or the head of the medical institution (where applicable) is responsible for study intervention accountability, reconciliation, and record maintenance (i.e., receipt, reconciliation, and final disposition records).

- Upon receipt of the study intervention(s), the Investigator or designee will confirm appropriate temperature conditions have been maintained during transit and any discrepancies are reported and resolved before use. Also, the responsible person will check for accurate delivery. Further guidance and information for study intervention accountability are provided in the Study Reference Manual.
- Only participants enrolled in the study may receive study intervention(s) and only authorized site staff may supply it. All study intervention(s) will be stored in a secure, environmentally-controlled, and monitored (manual or automated) area, per the labeled storage conditions, and with access limited to the Investigator and authorized site staff.
- Dispensing will be recorded on the appropriate accountability forms so that accurate records will be available for verification at each monitoring visit.
- Study intervention(s) accountability records at the study site will include the following:
  - Confirmation of receipt, in good condition and in the defined temperature range.
  - The inventory provided for the clinical study and prepared at the site.
  - The dose(s) each participant used during the study.
  - The disposition (including return, if applicable) of any unused study intervention(s).
  - Dates, quantities, batch numbers, container numbers, expiry dates, and the participant numbers.
- The Investigator site will maintain records, which adequately documents that participants were provided the doses specified in this protocol, and all study intervention(s) provided were fully reconciled.
- Unused study intervention(s) will not be discarded or used for any purpose other than the present study. No study intervention that is dispensed to a participant may be re-dispensed to a different participant.
- A Study Monitor will periodically collect the study intervention(s) accountability forms.

Further guidance and information for the final disposition of unused study intervention(s) are provided in the Study Reference Manual.

## 6.3 Measures to Minimize Bias: Study Intervention Assignment and Blinding

### 6.3.1 Study Intervention Assignment

In Part B, after completion of Cohort B0 and evaluation by the IDMC, participants will be randomly assigned to Cohorts B1, B2, and B3. Randomization to the cohorts will be stratified by site with a ratio of 1:2:1 to Cohorts B1, B2, and B3 using a computer-generated randomization list integrated in the electronic data capturing system.

Participants will be assigned a unique number (randomization number) in ascending numerical order at each study site. The randomization number encodes the participant's assignment to one of the 3 cohorts of the study, per the randomization schedule generated prior to the study. Open-label study intervention will be labeled with a unique medication number.

### 6.3.2 Blinding

The study will be open-label.

Parasitologists and laboratory personnel performing the microscopy and PCR will be blinded in order to minimize bias.

## 6.4 Study Intervention Compliance

When the individual dose for a participant is prepared from a bulk supply, the preparation of the dose will be confirmed by a second member of the study site staff.

When participants are dosed at the site, they will receive study intervention directly from the Investigator or designee, under medical supervision. The date and time of each dose administered in the clinic will be recorded in the source documents and recorded in the CRF. The dose of study intervention and study participant identification will be confirmed at the time of dosing by a member of the study site staff other than the person administering the study intervention. Study site staff will examine each participant's mouth to ensure that the study intervention was ingested.

## 6.5 Dose Modification

A single daily dose 660 or 500 mg M5717 is selected as the dose to be evaluated in Cohort B0/B1 and a daily dose of 660 or 500 mg will be administered daily for 2 days in Cohort B2 (see [Table 5](#)). After completion of Part A, and after completion of Cohort B0, the IDMC will have the option to recommend a dose adjustment for M5717 based on the exposure deviation from the predicted exposure, that will be supported by internal PK/PD analysis. This is planned to avoid unnecessary under or overexposures in any of the doses assigned across the two weight bands established.

**Table 5** M5717 Free Base Dosage for Part A and B (Cohorts B0/B1 and B2)

Body Weight	Part A		Part B			
	Equivalent Dose	Treatment Regimen	Cohort B0/B1		Cohort B2	
			Equivalent Dose	Treatment Regimen	Equivalent Dose	Treatment Regimen
Adolescents ≥ 24 to < 45 kg	NA	NA	500 mg	Daily for 1 day	500 mg	Daily for 2 days
Adolescents ≥ 45 kg	NA	NA	660 mg	Daily for 1 day	660 mg	Daily for 2 days
Adults	330 mg	Daily for 1 day	660 mg	Daily for 1 day	660 mg	Daily for 2 days

NA=not applicable.

The pyronaridine dose in Cohorts B0/B1 and B2 will be a maximum daily dose of 720 mg pyronaridine for participants with body weight ≥ 65 kg and will be adjusted to the weight bands as specified for Pyramax in the SmPC ([Pyramax SmPC](#), see [Table 6](#)). This dose of pyronaridine will be given together with M5717 on a daily basis for a single day (Cohort B0/B1, in total 720 mg) or for 2 days (Cohort B2, in total 1,440 mg).

**Table 6** Pyronaridine Tetraphosphate Dosage for Part A and B (Cohorts B0/B1 and B2)

Body weight	Part A		Part B			
	Number of Tablets and Dose	Treatment Regimen	Cohort B0/B1		Cohort B2	
			Number of Tablets and Dose	Treatment Regimen	Number of Tablets and Dose	Treatment Regimen
≥ 24 to < 45 kg	2 tablets = 360 mg/day	Daily for 1 day	2 tablets = 360 mg/day	Daily for 1 day	2 tablets = 360 mg/day	Daily for 2 days
≥ 45 to < 65 kg	2 tablets = 360 mg/day	Daily for 1 day	3 tablets = 540 mg/day	Daily for 1 day	3 tablets = 540 mg/day	Daily for 2 days
≥ 65 kg	2 tablets = 360 mg/day	Daily for 1 day	4 tablets = 720 mg/day	Daily for 1 day	4 tablets = 720 mg/day	Daily for 2 days

A daily dose of Pyramax of a maximum of 720 mg pyronaridine and 240 mg artesunate will be given in Cohort B3 for 3 consecutive days according to the SmPC ([Pyramax SmPC](#), see [Table 7](#)).

**Table 7** Pyronaridine-artesunate (Pyramax) Dosage for Part B (Cohort B3)

Body weight	Number of Tablets and Dose of Pyronaridine-artesunate	Treatment Regimen
≥ 24 to < 45 kg	2 tablets = 360 mg-120 mg/day	Daily for 3 days
≥ 45 to < 65 kg	3 tablets = 540 mg-180 mg/day	Daily for 3 days
≥ 65 kg	4 tablets = 720 mg-240 mg/day	Daily for 3 days

Details on the justification for selecting the doses are provided in Section 4.3.

This protocol allows some alteration from the outlined dosing schedule, but for M5717 the maximum daily dose will not exceed exposure achieved with the 1,440 mg dose in the FIH study. For pyronaridine the maximum daily dose specified in Section 6.1 will not be modified for each weight band.

No dose modifications are permitted at the participant level due to safety or tolerability reasons. If a participant in Cohorts B2 or B3 experiences a severe AE at the first or second day of treatment, the second and/or third day of treatment can be omitted according to Section 7.1 or judgment of the Investigator, but the dose cannot be reduced or delayed.

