## 2.3.1 Risk Assessment

Identified and Potential Risks of Clinical Significance	Summary of Data/Rationale for Risk	Mitigation Strategy
Study Intervention(s) (M5717, Pyronaridine)		
Lack of efficacy (ETF) and progression to severe malaria	In Part A, in which intermediate doses of the M5717-pyronaridine combination are evaluated, an ETF in around 2.5% to 40% of the population depending on the model used for the efficacy prediction could occur.	Close parasitemia monitoring is implemented in the Schedules of Assessments and rescue medication with standard of care will be applied once the treatment failure is confirmed by microscopy.
Overlapping liver enzymes increase and hepatotoxicity	Pyronaridine has been shown to induce transaminases increase in around 2% to 3% of the population, while M5717-induced mild, transient, non-dose related increases of transaminases, but there is an unknown risk of potentiation of such undesirable effects.	Specific monitoring of LFT has been established, patients with abnormal LFT at Baseline have been excluded, specific stopping criteria have been established between the dose increase from Part A to Part B, and before opening the randomized phase of Part B.
Overlapping central nervous system events	M5717 at high doses produced mild and transient CNS events (blurred vision and paresthesia), while Pyronaridine has been related to some neurological events (paresthesia and dizziness)	Specific monitoring of neurological signs and symptoms included in the participants' follow-up; exclusion of patients with known history of neurological diseases. A maximum dose was established for Part B so that predicted exposures will remain below those observed in participants with CNS events during the FIH study.
Overlapping gastrointestinal events	Both compounds, M5717 and pyronaridine have been shown through the nonclinical and clinical studies to induce gastrointestinal events such as nausea, vomiting, and abdominal pain.	Specific monitoring of the severity and duration of gastrointestinal symptoms is included in the participants' follow-up.
Study Procedures		

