#### **4.3                    Justification for Dose**

Based on data from a Phase I study (MS201618\_0013), the M5717 monotherapy at doses up to 1,440 mg (1,800 mg succinate) were considered safe and well tolerated. The exposure observed

at that dose has been set as the maximum exposure for the study as a 1-day or 2-day dosing regimen.

As this is the first administration of M5717 in combination with pyronaridine, a reduced dose was chosen for the safety run-in (Part A). From an ethical perspective it is important to ensure, a minimum efficacy for those participants treated with an intermediate dose of the M5717-pyronaridine combination. For this purpose, a preliminary PK/PD modeling was performed to assess the percentage of participants reaching 95% ACPR28 efficacy (data on file). This model suggests that with a single dose of 330 mg M5717 combined with 360 mg pyronaridine, the median ACPR28 efficacy is predicted to be between 59.1% and 92.2%. In addition, the dose selected is providing a large safety margin for individual compounds (M5717: 330 mg versus 1,440 mg, pyronaridine: single dose 360 mg versus 720 mg for 3 days) compared to the doses evaluated in the FIH/clinical studies. In particular, the AUC and  $C_{max}$  (90% prediction interval) associated with single and 2-day administration of M5717 is within the safe and tolerable 1,400 mg exposures. For pyronaridine, the dose selected for the safety run-in group was based on minimizing the risk of liver enzymes increase potentiation which remains the only relevant safety risk identified for this molecule.

[figure not shown]
Single doses of 660 mg M5717 (= 800 mg M5717 succinate) were shown to be efficacious in monotherapy in the FIH study. This dose was selected as the target dose for the pyronaridine combination in Part B. To account for the broad body weight range in the target population of adolescents and adults between 12 and 55 years, dose stratification by body weight was introduced. Exposure simulations based on the population PK model predict exposures for all body weight categories, and for both 1-day ([Figure 1](#)) and 2-day ([Figure 2](#)) regimens that are below the maximal exposure achieved in the FIH Study (ctr-ms201618-0013) after administration of the maximal dose of 1,400 mg, and that was found to be safe and well tolerated.

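### The M5717 exposure ceiling is set for the whole 1- or 2-day regimen in Protocol Section 4.3 but only for the daily dose in Section 6.5, so the limit on raising a 2-day dose is not uniquely defined

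*Protocol*

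**What the plan says.** Protocol Section 4.3 reports that "M5717 monotherapy at doses up to 1,440 mg (1,800 mg succinate) were considered safe and well tolerated" and that the exposure observed "at that dose has been set as the maximum exposure for the study as a 1-day or 2-day dosing regimen". The same section applies this to the regimen as a whole: simulated 1-day and 2-day exposures are both said to lie within the 1,440 mg exposure, and the Figure 2 caption (2-day dosing) gives a 1,440 mg single dose as the reference band.

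Protocol Section 6.5 permits some alteration of the dosing schedule, with the limit that "for M5717 the maximum daily dose will not exceed exposure achieved with the 1,440 mg dose in the FIH study". It states no limit for the 2-day total and does not say whether AUC or Cmax is meant. The same section lets the IDMC recommend an M5717 dose adjustment after Part A and after Cohort B0. Section 4.1 makes clear that the dose for later cohorts may go up as well as down.

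The reference dose is 1,440 mg in Sections 2.3.2, 4.3 and 6.5 and in the captions of Figures 1 and 2. Section 4.3 also says that the AUC and Cmax "associated with single and 2-day administration of M5717 is within the safe and tolerable 1,400 mg exposures", and in its next paragraph again gives 1,400 mg, as the maximal FIH dose. The free-base equivalents differ too: "Single doses of 660 mg M5717 (= 800 mg M5717 succinate" in 4.3 (the same pair is in 2.2), against 1,440 mg for 1,800 mg succinate. Section 2.3.2 gives 640 mg for the dose that cleared parasites without recrudescence, where 2.2 has 660 mg for the curative dose.

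**The concern.** For a single-day regimen, a limit on the daily dose and a limit on the regimen are the same thing. For two days they are not. Section 4.3 bounds the exposure of the regimen. The wording of 6.5 bounds each day's dose against the exposure of a single 1,440 mg dose and leaves the sum unbounded. The looser wording is in the section that an IDMC would consult when changing a dose.

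At stake is whether an increase for a 2-day cohort could satisfy 6.5 and still exceed what 4.3 calls the study maximum. Because 6.5 names no metric and 4.3 carries two labels for the reference dose, a committee could not apply the rule without first interpreting it.

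**Working it through.** **Inputs.** Planned 2-day dose: 660 mg daily for 2 days (500 mg below 45 kg, chosen in 4.3 to give exposure similar to 660 mg in adults). Reference dose: 1,440 mg, or 1,400 mg where 4.3 says so. Half-life: 155 h, from the contraception criterion in Section 5.1. It reproduces the 62 days given there (5 x 155 / 24 + 30 = 62.3), but it is not attributed to M5717 alone, so it is an assumption here.

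**The plan's own check.** The prediction intervals come from a population PK model whose parameters are not given and whose figures are not shown, so they cannot be reproduced. The typical value can be checked under dose proportionality: 2 x 660 = 1,320 mg; 1,320 / 1,440 = 0.917; 1,320 / 1,400 = 0.943. Both are consistent with the statement that the planned 2-day regimen lies within the ceiling.

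**Two-day AUC permitted by each rule.**
- Section 4.3: total AUC at most 1.00 x AUC(1,440 mg). If dose-proportional, this corresponds to 1,440 / 2 = 720 mg/day, which is 9% above 660 mg (720 / 660 = 1.09).
- Section 6.5, literal and alone: each day up to AUC(1,440 mg), so by superposition a total of 2.00 x AUC(1,440 mg). This corresponds to 1,440 mg/day, which is 118% above 660 mg (1,440 / 660 = 2.18).
- Ratio: 2.00 / 1.00 = 2.0. Mixing the two reference doses gives 2,800 / 1,440 = 1.94 to 2,880 / 1,400 = 2.06. The ratio itself needs superposition only; the mg/day equivalents also need dose proportionality.

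These equivalents show the size of the gap. They are not proposed doses.

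**If 6.5 is meant to include carry-over from Day 1.** In a one-compartment model the peak after the second dose is 1 + 2^(-24/155) = 1.898 times a single-dose peak. Holding that peak to the 1,440 mg level gives 1,440 / 1.898 = 759 mg/day, and the 2-day AUC relative to the 4.3 limit is 2 / 1.898 = 1.05. With other assumed half-lives the factor is 1.50 at 24 h and 1.946 at 300 h, so the AUC ratio is 2 / 1.50 = 1.33 and 2 / 1.946 = 1.03.

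**Sensitivity to dose proportionality.** If AUC varies as dose to the power b, the planned regimen uses 2 x (660 / 1,440)^b of the 4.3 limit: 1.07 at b = 0.8, 0.99 at 0.9, 0.92 at 1.0 and 0.85 at 1.1. The documents give no value for b.

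**Labels.** 1,440 / 1,400 = 1.029, a 2.9% difference. Salt factors: 660 / 800 = 0.825 and 1,440 / 1,800 = 0.80. At 0.80, 800 mg succinate is 640 mg, the figure in 2.3.2; at 0.825 it is 660 mg, the figure in 2.2.

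**The case against.** The best defence is that the two sections apply together. Section 4.3 speaks of the maximum for the study, 6.5 refers to 4.3 immediately before stating its own limit, and nothing in 6.5 sets 4.3 aside. On that reading the stricter limit governs. This is a fair reading, but the cross-reference is for the justification of the selected doses and does not import a second cap. A rule for changing doses should not depend on the reader finding the stricter limit elsewhere.

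It is also fair that the sentence in 6.5 mixes dose and exposure and may be meant to include carry-over, which nearly closes the gap under the assumed half-life. The text does not say so. A large increase is unlikely as well: 6.5 ties adjustment to deviation from predicted exposure, and further decision criteria are assigned to an IDMC charter that is not among these documents.

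Four stronger readings are tempting but not supported:
- That participants were exposed under the looser rule. SAP Section 7 says Cohorts B1, B2 and B3 were not enrolled, and SAP Section 13 describes a single dose on Day 1, for which the two limits coincide.
- That the planned 2-day regimen breaches the ceiling. Under dose proportionality it does not, and 4.3 reports that the simulated intervals lie within it.
- That an adjustment allowed by 6.5 would defeat the protection against CNS events. Section 2.3.1 says that "A maximum dose was established for Part B so that predicted exposures will remain below those observed in participants with CNS events", but it names neither 1,440 mg nor Sections 4.3 or 6.5, and the documents do not give the exposures at which those events occurred. It is a separate bound; a link to this ceiling is inference.
- That the 1,400 mg label or the salt factors move the ceiling. The limit is the exposure observed at an identified FIH dose, and relabelling the dose changes only its mg equivalent. The 1,400 mg figure may be a typing error.

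**Conclusion.** The inconsistency is real, and it lies in the protocol text. Section 4.3 bounds the regimen and 6.5 bounds the day. On the literal wording of 6.5 taken alone, the permitted 2-day AUC differs by a factor of 2.0. If carry-over is meant to count, it differs by about 5%, resting on a one-compartment model and a 155 h half-life that the protocol does not assign to M5717. The twofold figure is a statement about AUC on one reading, not a finding that the protocol as a whole permits double exposure.

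The conflict matters only for an upward adjustment of a 2-day regimen. It had no consequence for the participants or analyses of this study. The labelling discrepancies are small and secondary, but they sit in the paragraphs that define the ceiling. The documents do not settle which ceiling is intended, and this review takes no view on which is clinically right.

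**What to change.** Reconcile Sections 4.3 and 6.5 so that one ceiling is worded the same way in both. It should state whether it applies per daily dose or to the whole regimen (and, if per day, whether carry-over counts), which FIH dose it refers to as free base, and which exposure metric is compared with it. Correct the 1,400/1,440 mg discrepancy in 4.3, use one succinate conversion throughout, and reconcile 640 mg in 2.3.2 with 660 mg in 2.2. Do this before the rule is used for any 2-day dose adjustment, here or in a later protocol that takes over the wording. The sponsor sets the clinical value.

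The cost is protocol wording, with the IDMC charter aligned to it; no extra data are needed. The downside is that the room for adjustment may be narrower than 6.5 now implies.
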